Title: Prone Versus Supine Positioning and the Impact on Bronchopulmonary Dysplasia in Very Low Birth Weight Infants

NCT04890158

IRB Approved: 27-OCT-2021

Title: Standardized prone positioning compared to usual positioning of very low birth weight infants receiving respiratory support and the effect on bronchopulmonary dysplasia (bpd).

Hypothesis: Standardized prone positioning in ventilated, very low birth weight, preterm infants will lead to a reduction in moderate (Grade 2) to severe (Grade 3) BPD as assessed at 36 weeks post conceptional age (PCA).

Background: Bronchopulmonary Dysplasia (BPD) occurs most often in those infants born less than 32 weeks gestation and in those weighing less than 1500 grams at birth. While its definition is somewhat variable, the diagnosis usually rests on the duration of need for oxygen and use of positive pressure ventilation. That is, oxygen use for ≥ 28 days, before 36 weeks PCA or discharge, whichever is earlier, coupled with use of positive pressure ventilation including invasive (via endotracheal tube or tracheostomy tube) as well as non-invasive modalities such as nasal continuous positive airway pressure (NCPAP), non-invasive positive pressure ventilation (NIPPV), nasal cannula (NC) or high flow nasal cannula (HFNC).⁽¹⁾ With three clinical classifications of severity, mild, moderate and severe, we find that 16% of infants in large cohort studies with a weight less than 1000 grams at birth will have severe BPD.⁽²⁾ However depending on the definition of "severe BPD" used, it could encompass up to one third of all premature infants⁽¹⁾. For 2019, The Children's Hospital at Montefiore-Weiler Division Neonatal Intensive Care Unit had 34 of 107 (31.7%) very low birth weight infants (VLBW), i.e those born less than 1500 grams, who were diagnosed with moderate to severe BPD. BPD was defined as utilization of a ventilator or continuous positive airway pressure (CPAP), use of HFNC or regular flow NC >2 L at 36 weeks PCA. Of the 107 VLBW infants identified, 9 died.

There is considerable practice variation in the respiratory management of BPD patients.

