There was no statistical improvements noted for acute respiratory distress, however a decrease in respiratory system resistance was noted for infants with BPD during prone positioning.(9) In 2018 Zhong and colleagues randomized 79 preterm mechanically ventilated infants to supine vs prone positioning. Fraction of inspired oxygen (FiO₂), peak inspiratory pressure, mean inspiratory pressure, and duration of ventilation were significantly lower in the prone group than in the supine group (P < 0.05).(10)

There were no reports of adverse events in pediatric patients in the aforementioned studies. However in adult patients adverse effects such as pressure sores and tracheal obstruction were reported.

While the prior studies have shown temporal benefit for preterm, ventilated infants who undergo prone positioning, many are short term studies and none have assessed its impact on severity of BPD.

Objective: We aim to evaluate in this pilot study whether standardized prone positioning compared to usual positioning improves moderate to severe BPD rates as assessed at 36 weeks post conceptional age in VLBW preterm infants with BPD.

Material and methods

Study plan:

We aim to enroll and randomize infants born at less than 1500 grams at birth, who remain

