on positive pressure support for at least 7 days after birth AND/OR on any other respiratory device such as nasal cannula with flow rates greater than 2LPM receiving supplemental oxygen of greater than 21% for at least 7 days after birth. Positive pressure for the purposes of this study is defined a nasal cannula delivering a flow of 2 LPM or higher, continuous positive airway pressure (CPAP), non-invasive positive pressure ventilation or non-invasive mechanical ventilation (NIPPV/NIMV), as well infants who are intubated or have a tracheostomy for oxygenation and ventilation related to their lung disease, irrespective of the mode of ventilation. We will exclude infants who were previously on room air without a respiratory device who were intubated for the purposes of surgery and were not receiving respiratory support as defined above prior, those intubated for other airway issues such as tracheal stenosis, broncho- or tracheomalacia, etc and not for the management of BPD. Additional patients to be excluded include those with suspected or proven genetic or other major congenital anomalies that may impact cardiac and lung function including cardiac and lung anomalies, as well as those at the time of enrollment who require surgeries that will impact their ability to be placed in prone positioning (eg gastroschisis, omphalocele, etc).

Patients meeting the aforementioned criteria will be assigned to 1. usual care in which positioning and duration in each position is random per usual nursing routine OR 2. Receive standardized scheduled daily prone positioning starting on day of life 7. As part of normal developmental care, most infants are evaluated and have care rendered (touch-time), if stable, and repositioned at set three-hour intervals to permit uninterrupted sleep and/or rest. The hands-off interval will be maintained throughout the study interval. Infants randomized to the standardized scheduled daily prone positioning will be placed in prone body position for a total of 6 hours daily, that is prone position for 3 hours, followed

by supine positioning for 3 hrs, then placed in prone position for another 3-hour interval. Standardized daily positioning will occur for randomized patients until 36 weeks or discharge whichever is first. If needed, position aids, which are part of the normal care routine in our ICU, may be used to facilitate maintenance of prone or supine positioning.

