Identification: Each day, NICU admissions will be reviewed via the electronic medical record and infants who are born with a birthweight of less than 1500 grams will be identified. On day of life (DOL) 5-7, of those infants identified, those parents of infants who are still maintained on positive pressure ventilation and or >21% FiO₂, will be approached and consented for inclusion in the study.

Consent: Families will be approached in person in the Neonatal Intensive Care Unit or Post-Partum Unit between DOL 5-7 and consent obtained for participation in the study by [name] or [name]. One parental signature will be required. Written study material and copies of consent forms will be provided for families to keep. There will be no cost to the patient and no remuneration offered. Families may withdraw consent at any point of the study. See separate consent form, appendix 1.

Procedures: Consent will be obtained between DOL 5-7. Subjects will undergo block randomization. Once randomized, those patients who are assigned to standardized, scheduled prone positioning, will be placed in prone position, with the head turned either right or left per nursing or patient desire, for a total of 6 hours daily, during daytime hours, if clinically stable. They will be placed in prone position for 3 hours, followed by supine positioning for 3 hours, then placed in prone position for another 3-hour interval. If needed, position aids, which are part of the normal care routine in our ICU may be used to facilitate maintenance of prone or supine positioning. If an infant is felt to be too unstable, or significantly

intolerant of prone positioning, they may be positioned per nursing or patient comfort. If infant was already in the prone position per nursing routine prior to the start of prone positioning per study protocol, we will await change to a different position before initiating study protocol for infants assigned to scheduled prone positioning. This is to avoid infants being placed in prone position for > 3 consecutive hours at a time). Alternating between supine and position allows us to detect any short term immediate changes in oxygenation and vital signs attributable to a change in positioning between prone and supine.the two positions.

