We aim to record and collect the following data once weekly on the weekly anniversary of the infantâ€™s first study prone positioning and the date of randomization onto the study for those study participants who were randomized to usual care: transcutaneous CO₂ (TCO₂) if available or PCO₂ from any blood gas, SaO₂ from cardiopulmonary monitors, PaO₂ from arterial blood gases within 1 hour of positional change (if available), ventilator or other respiratory support modality settings and direction of changes within 1 hour of positional change. Specifically, percent change in inspired oxygen, change in ventilator rate (breaths per minute), tidal volume (milliliters), peak inspiratory pressure (cm H₂O), positive end expiratory pressure (cm H₂O) and the number of episodes of oxygen desaturations will be collected. Current comorbidities, most recent chest x-ray findings within a 7day interval will also be documented once weekly.

Other data: duration of time on any respiratory support (days), duration of use of endotracheal tube, non-invasive positive pressure ventilation (NIPPV) and continuous positive airway pressure (CPAP), time to FiO₂ of 21% (irrespective of type of respiratory interface), type of medications to treat BPD (use of oral, inhaled or intravenous postnatal steroids for mitigation of BPD, caffeine, diuretics daily or intermittent), presence of pulmonary hypertension as documented by echocardiogram, use of sedatives and analgesics, pharmacologic treatment of

GERD, use of inhaled nitric oxide on DOL 7 or later. Additionally, the mode of ventilation at 7 days after birth, DOL when maximal feeds achieved (total fluids of 160 milliliters per kilogram per day), DOL at which feeding by mouth was initiated and DOL at which feeds were administered by mouth only, diagnosis of plagiocephaly, and the duration of NICU stay. Demographic data of interest include gestational age at birth (weeks), maternal comorbidities, infant comorbidities, growth status (small, appropriate or large for gestational age), weight at birth (kilograms) and use of antenatal steroids.

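### Entry has no gestational-age limit, so infants born from 34w0d can be randomised with at most a week of possible treatment before 36 weeks, and from 35w0d with none

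*Combined protocol and SAP*

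**What the plan says.** **Entry.** The weight limit is set at the start of the Study plan in Material and methods, in these words: "We aim to enroll and randomize infants born at less than 1500 grams at birth, who remain". The respiratory condition that follows is to be "on positive pressure support for at least 7 days after birth", or to have needed another respiratory device with supplemental oxygen for the same period. The exclusions cover intubation only for surgery or airway problems, genetic or major anomalies affecting heart or lung, and surgery that prevents prone placement. None refers to gestational age. The daily screen under Identification also uses weight: "infants who are born with a birthweight of less than 1500 grams will be identified". The word preterm occurs in the Hypothesis and in the Objective ("improves moderate to severe BPD rates as assessed at 36 weeks post conceptional age in VLBW preterm infants with BPD"), but with no week attached and not as a criterion.

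**Treatment window.** The Study plan starts scheduled positioning on day of life 7 and closes it as follows: "Standardized daily positioning will occur for randomized patients until 36 weeks or discharge whichever is first".

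**Outcome.** Evaluations and measures assigns the primary outcome from the support in use at 36 weeks post conceptional age. Invasive ventilation is Grade 3. Nasal CPAP, NIPPV, high-flow cannula or cannula flow above 2 L/min is Grade 2. No minimum duration of oxygen or of study participation is required.

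**Background.** BPD "occurs most often in those infants born less than 32 weeks gestation", and the same sentence also names birth weight below 1500 g. The usual diagnosis is said to rest on "oxygen use for ≥ 28 days, before 36 weeks PCA or discharge, whichever is earlier" together with positive pressure support, but the definition is acknowledged to vary.

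**Analysis.** Statistical Considerations plans 30 infants per arm, analysed by intention to treat and read as exploratory. The Randomization section describes variable blocks and states no stratification.

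**The concern.** Weight is an entry limit that does not fix how long an infant can be treated. The end of treatment and the outcome assessment are both tied to 36 weeks, so the time available is whatever remains between day of life 7 and that date. A growth-restricted infant can weigh under 1500 g at a gestational age that leaves little or no time.

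The pilot exists to give a preliminary effect size. An infant with no treatment window cannot contribute to one, whichever arm it joins. From 35w0d the difficulty is sharper: entry and outcome can rest on the same support, so the primary outcome may be settled before positioning could begin. Because the analysis is by intention to treat, such infants remain in the comparison once randomised. Entry is therefore the place to deal with them.

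**Working it through.** **1. The plan's own precision figure.** Inputs from Statistical Considerations: 31% and 21%, 30 per arm.

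Half-width = 1.96 × √(0.31 × 0.69/30 + 0.21 × 0.79/30) = 1.96 × √0.01266 = 0.2205, or 22 points. The stated figure reproduces, and this point does not alter it.

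**2. Treatment window by gestational age at birth.** Inputs from the Study plan: start on day of life 7, end at 36 weeks.

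- Days from birth to 36w0d = 7 × (36 − gestational age in weeks)
- Longest treatment window = that figure − 7, and not below zero

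| Birth at | Days to 36w0d | Longest window (days) |
|---|---|---|
| 24w0d | 84 | 77 |
| 28w0d | 56 | 49 |
| 31w6d | 29 | 22 |
| 32w0d | 28 | 21 |
| 32w1d | 27 | 20 |
| 33w0d | 21 | 14 |
| 33w6d | 15 | 8 |
| 34w0d | 14 | 7 |
| 34w6d | 8 | 1 |
| 35w0d | 7 | 0 |
| after 35w0d | 6 or fewer | 0 |

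These are maxima, since discharge can end positioning sooner. If birth is counted as day 1, each window up to 35w0d gains one day, and the pattern is unchanged.

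**3. Where entry and outcome meet.** An infant born at 35w0d reaches day of life 7 on the day it reaches 36w0d. If it is on CPAP or NIPPV, that support satisfies the entry rule and also meets Grade 2; if it is intubated, Grade 3. For later births the 36-week date falls before day of life 7, inside the qualifying period itself. The overlap is not complete: a cannula at exactly 2 L/min qualifies for entry but is Grade 1.

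**4. The 28-day description in the Background.** Only births at or before 32w0d have 28 days before 36w0d. Later births cannot meet that description, though they can meet the trial's own endpoint.

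**5. Size of the dilution.** The documents give no gestational-age distribution. Assume a share f of infants has no usable exposure, is equally common in both arms in expectation, and shows no difference between arms. The expected difference is then 10 × (1 − f) points.

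- f = 3% (about 2 of 60): 10 × 0.97 = 9.7 points
- f = 10% (6 of 60): 10 × 0.90 = 9.0 points

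If the unexposed infants also have the 31% rate, the intervention-arm rate is 21.3% or 22.0%, and the half-width is 22.1 or 22.2 points.

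**The case against.** The strongest reply is that the rule matches the trial's own frame. The Background names birth weight below 1500 g as a risk marker. The 2019 site rate (34 of 107) was counted in all such infants with no gestational limit, and by a 36-week support definition close to the trial endpoint. An affected infant must be under 1500 g, on support for a week and free of the excluded anomalies. The dilution is small beside ±22 points in a study labelled exploratory. Gestational age is recorded, and the regression models may adjust for imbalance. All of this stands, and it limits the size of the point.

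It does not close the gap. Adjusting for gestational age, or reporting by it, cannot supply treatment time that never existed. It could also be said that short stays still inform the physiological comparisons around position changes. That is fair for infants with some days of treatment, but not for those with none.

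A reader might infer more than the documents support:

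- **That every birth after 32 weeks is nearly untreated.** Births from 32w1d to 33w6d have 8–20 days.
- **That events in later-born infants are not the disease under study.** The 28-day description is background; the endpoint in Evaluations and measures has no duration requirement, so scoring these infants follows the trial's rule.
- **That recording small-for-gestational-age status shows late births are expected.** It is a baseline descriptor at any gestational age.
- **That a few such infants distort the arms in a special way.** One event moves an arm's rate by 1/30 = 3.3 points, but that is true of any infant.

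**Conclusion.** The point holds within a narrow range. As written, the criteria admit infants born at 34w0d–34w6d with 1–7 possible treatment days and infants born at 35w0d or later with none; for the latter, qualifying support can itself be the Grade 2 or 3 outcome. Infants born at 32w1d–33w6d are not invalid entrants.

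The number affected is unknown and, given the weight and support requirements, probably small. The expected consequence is modest dilution: 10 points becomes 9.7–9.0 on an assumed 3–10% share. It is not systematic bias, because allocation is random, although no stratification is stated and chance imbalance between arms of 30 is possible. The date arithmetic is firm; the share is an assumption. The change is worth making because it is cheap and the affected infants cannot inform the estimate the pilot is meant to produce, not because the trial's conclusions are at risk without it.

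**What to change.** Add one entry criterion to the Study plan, and repeat it under Identification and Consent, that guarantees a usable window between day of life 7 and 36w0d. Gestational age at birth below 34w0d, alongside the weight limit, gives at least 8 days. State whether birth counts as day 0 or day 1, so that the window is unambiguous.

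A limit below 32w0d, giving at least 22 days, is an option for the sponsor. It fits the very preterm population named in the title of the source cited for the endpoint (reference 11), but the documents do not compel it. It would also drop infants with one to three weeks of possible treatment. Nor would it align the endpoint with the 28-day description, since being 28 days old is not the same as 28 days of oxygen.

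**Cost.** One line in the criteria and in the daily screen; gestational age at birth is already collected. A few growth-restricted later-born infants would not be enrolled, so recruitment may be slightly slower. The 31% planning rate comes from all very low birth weight infants and should be re-derived for the restricted group, with the precision statement updated to match.

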Personnel: Neonatologists [name] and [name] will be responsible for consenting families and determining randomization assignment. Bedside nurses along with respiratory therapists will be responsible for position changes and documentation of physiologic metrics and vital signs as part of the normal ICU care practice. [name] will collect study data for analysis. Nurse practitioner [name], BSN, DNP, will be responsible for assigning the primary outcome of moderate or severe BPD, at or after 36 weeks post conceptional age. She will be provided a list of study participants identified only by study number at 36 weeks post conceptional age, their respiratory support parameters and will assign the primary outcome of moderate (Grade 2) or severe (Grade 3) BPD.

Randomization: Block randomization with variable block sizes will be performed in order to ensure equal sample sizes over time. The treatment (standardized prone positioning) ratio to control (usual positioning) ratio will be 1:1. The randomization list will be generated by the study statistician and will be maintained under locked conditions. Blinding of staff is inherently not feasible as scheduled prone position changes are obvious to caretakers.

Evaluations and measures: Incidence and severity of BPD will be assessed at 36 weeks post conceptional age. As part of usual NICU care, infants, especially those on respiratory support have vital signs and other physiologic parameters recorded routinely every 3 hours,

but this may occur as frequently as every hour in the sickest infants. Enrolled infants will have physiologic data and vital signs evaluated and recorded at start of hands-on time, at the 1 hour mark after scheduled position change to prone, at the time of switch to supine, 1 hour after 2nd switch to prone position, and at the time of conclusion of study positional changes. For infants randomized to usual care, we will record similar data from a period of 3 hands-on intervals (total of 9 hours).

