that patient characteristics are distributed similarly across groups. The difference between the intervention and control arms in the rate of BPD at 36 weeks post-conceptional age and other outcomes will be estimated, along with corresponding 95% confidence intervals. In exploratory analyses, the chi-square test will also be applied to assess whether the rates of BPD and other binary outcomes are significantly different between groups, and the two-sample t-test will be used compare the mean values of continuous variables measured at a specific visit. Logistic and linear regression models will also be fit to the data to adjust for any baseline characteristics that are not balanced across groups despite randomization. Weekly physiologic, ventilator and other clinical data will be obtained and analyzed using generalized linear mixed models, with the logit link for binary outcomes and the identity link for continuous outcomes, to account for the correlation in repeated measures from the same infant. Missing data will be handled by analyzing the available data as well as by multiple imputation using chained equations. All analyses will be based on the intent-to-treat approach, and results will be viewed as exploratory and hypothesis generating.

We plan to randomize a total of 60 patients 1:1 to intervention and control (N=30 per arm). Since this is a pilot trial, the goal is to obtain preliminary data on effect sizes. Therefore, formal power calculations were not performed. With 30 patients per arm, the precision, as measured by the width of the 95%CI, with which the true intervention effect (i.e., difference between groups) can be estimated is +/- 25% or better. For example, to gauge the magnitude of the primary outcome of BPD incidence and the potential benefit of standardized prone positioning, we evaluated 2019 BPD rates in our NICU. There were 107 patients described as VLBW at birth. Of those, 34 infants developed moderate to severe BPD, a rate of 31%. If the observed BPD rate is reduced to 21% in the intervention arm for a between group difference of

10%, then the corresponding width of the 95% CI for the true difference will be +/- 22%. We anticipate performing this pilot study over 2-3 years to account for yearly variations in the admission of VLBW patients.

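### The primary BPD risk difference is planned without a pre-specified birth-weight adjustment, so a removable part of its chance error stays in; a stratified estimate would take it out at almost no cost.

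*Combined protocol and SAP*

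**What the plan says.** Under Randomization the protocol states: "Block randomization with variable block sizes will be performed in order to ensure equal sample sizes over time". The ratio is 1:1, and the list is spoken of in the singular: "The randomization list will be generated by the study statistician and will be maintained under locked conditions". No stratification factor appears anywhere in the document.

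Under Statistical Considerations the lead estimate is described as "The difference between the intervention and control arms in the rate of BPD at 36 weeks post-conceptional age", with a 95% confidence interval. The size is given as "We plan to randomize a total of 60 patients 1:1 to intervention and control (N=30 per arm"). The precision example starts from the unit's 107 infants of 2019: "Of those, 34 infants developed moderate to severe BPD, a rate of 31"%. It continues "If the observed BPD rate is reduced to 21% in the intervention arm for a between group difference of" 10 points, and "then the corresponding width of the 95% CI for the true difference will be +/- 22"%.

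The same section first compares baseline variables by arm. It then plans logistic and linear regression to adjust for those that turn out not to be balanced. It names no covariate and gives no rule for what counts as unbalanced. Results are labelled exploratory.

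The only weight-specific risk in the document is in the Background: "16% of infants in large cohort studies with a weight less than 1000 grams at birth will have severe BPD". Birth weight is used to identify eligible infants and is on the list of demographic data (Evaluations and measures).

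**The concern.** Blocking controls how many infants go to each arm, not which infants. All infants below 1500 g who are still on support are eligible. If BPD risk differs between the smaller and larger infants, a chance surplus of small infants in one arm shifts the raw rate difference in a known direction.

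The planned regression is a partial safeguard with three weaknesses. The covariates are picked after the imbalance is seen, the selection rule is open, and for a binary outcome the logistic model gives an odds ratio, whereas the stated estimate is a difference in rates. An adjusted result could therefore not simply replace the main one.

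The stated goal of the pilot is preliminary data on effect sizes, so the precision of that one difference is what the trial delivers.

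**Working it through.** **1. The plan's own figure.** With 30 per arm and 31% versus 21%:

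- SE = sqrt(0.31×0.69/30 + 0.21×0.79/30) = sqrt(0.00713 + 0.00553) = 0.1125.
- Half-width = 1.96 × 0.1125 = 22.1 points. The stated 22 is reproduced.
- At 50% versus 50% the half-width is 25.3 points, which matches the stated worst case of 25.

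**2. How far the arms can differ in birth weight.** Let q be the share of infants below 1000 g. With 30 of 60 per arm, the SD of the between-arm difference in that share is sqrt(q(1−q) × (2/30) × (60/59)):

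- q = 0.4: 12.8 points.
- q = 0.5: 13.0 points.

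In simulated permuted blocks (sizes 2, 4 and 6 assumed), an imbalance of at least 20 points occurred in 14-15% of trials.

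**3. What that does to the BPD difference.** Let g be the risk gap between the weight bands. The shift is g times the imbalance in share. The documents do not give g or q, so both are assumptions, with overall risk held at 31%. For q = 0.5 the SD of the shift is:

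- g = 10 points: 0.10 × 13.0 = 1.3 points.
- g = 20 points: 0.20 × 13.0 = 2.6 points.
- g = 40 points: 0.40 × 13.0 = 5.2 points.

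A one-SD shift reaches 5 points only when g is 0.05/0.130 = 38 points (39 at q = 0.4). At g = 40 the imbalance accounts for (5.2/11.25)² = 0.21, about one fifth of the variance already in the interval.

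**4. Simulation, N = 60, 40-50% of infants below 1000 g.** The last column compares a Mantel-Haenszel risk difference with the raw difference, both on the single unstratified list.

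| Assumed gap | Trials with a shift of at least 5 points | Variance cut from the stratified analysis |
|---|---|---|
| 10 points | about 0% | none (loss of up to about 1%) |
| 20-23 points | 5-9% | about 5% (at 23 points: 45% v 22%) |
| 38-48 points (55% v 15%, 50% v 12%, 55% v 7%) | 34-38% | 16-26% |

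An exact calculation with the number below 1000 g fixed at 30 gives 7% at a 20-point gap, 20% at 30 and 44% at 40. The last is higher than the simulated 34-38% because a fixed even number lets the arms differ only by 0, 2, 4 and so on, and a difference of four already counts. When the number varies, half the trials have odd differences and need five.

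**5. Which change brings the gain.** With stratified lists as well as the stratified analysis, the cut at gaps of 38-48 points is 16-29%, against 16-26% for the analysis alone. The lists add about 0-4 points.

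**6. In terms of the interval.** As a rough guide, a cut of 16% takes the half-width to 22.1 × sqrt(0.84) = 20.3 points, and a cut of 26% to 22.1 × sqrt(0.74) = 19.0. That precision would otherwise need 60/0.84 = 71 or 60/0.74 = 81 infants. At a 5% cut the half-width is 22.1 × sqrt(0.95) = 21.5.

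**The case against.** The strongest case against is that the plan already deals with this. It checks baseline balance, collects birth weight and gestational age, and adjusts for what is unbalanced. It is also a pilot with exploratory results and no power calculation, and its interval already contains the chance imbalance. Even after the best-case gain, the interval is far too wide to settle a 10-point difference.

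Most of this stands. It rules out three stronger readings that a reader might infer.

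- **That the unstratified list biases the comparison.** It does not; the imbalance is random and equally likely to favour either arm.
- **That imbalance will typically shift the result by half or more of the hoped-for effect.** The 10 points are an example for precision, not a target, and a typical shift reaches 5 points only if the risk gap is near 40 points. No such gap is in the documents. The 16% in the Background is for severe BPD only, with no figure for 1000-1499 g.
- **That the randomisation list is what must change.** Nearly all the gain comes from the analysis.

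The objection does not answer the open choice of covariates or the mismatch of scale. Both are weaker than one factor named in advance, and both can be cured in one sentence.

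Birth weight is not the only possible factor: gestational age and ventilation mode at day 7 are also collected. Birth weight is suggested because it defines eligibility, is known before randomisation, and is the one factor for which the Background cites a specific risk group.

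**Conclusion.** The point holds as a cheap improvement in precision, not as a flaw that invalidates the trial. The primary difference should be adjusted for a prognostic factor named in advance, on the scale on which it is reported.

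The benefit runs from nothing at a 10-point risk gap, through about 5% of variance at 23 points, to 16-26% at 38-48 points. The conclusion rests on assumed risks by weight band, an assumed 40-50% below 1000 g, assumed block sizes, and an overall risk of 31%. That last figure comes from all 107 infants of 2019 rather than from those still on support at about day 7, so neither the base rate nor the gradient is known for the infants to be enrolled. At worst the stratified estimate costs about 1% of variance.

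**What to change.** Add one sentence to Statistical Considerations, before outcomes are compared by arm: the primary risk difference and its 95% confidence interval will be a Mantel-Haenszel estimate stratified by birth weight (below 1000 g; 1000-1499 g). This replaces covariates chosen after seeing imbalance for the primary outcome. It needs no new data and works on the existing list.

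If enrolment has not begun, the statistician can also issue two permuted-block lists by the same strata, keeping the variable block sizes. This gives visible balance in the baseline table and about 0-4 further points of variance reduction. The price is a second list, and arm totals that may differ by one or two infants because of incomplete blocks. If enrolment has begun, leave the list as it is; the stratified analysis is enough.
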